- Collaborating with monitors during the course of the study.
- All medical documents related to the study must be sent to Espad Pharmed Darou Co. at the conclusion of the study. A copy of these documents may be retained by the investigator.
- All medical documents related to the study must be kept by the investigator for the duration of the study and for five years following its completion.
- Confidentiality of the protocol and study data must be maintained, with no disclosure without written permission from Espad Pharmed Darou Co. and the principal investigator, except as necessary for obtaining informed consent from individuals to whom the product will be administered.

Introduction:

Submental fat (SMF) is considered aesthetically unappealing and can have a negative psychological impact on patients (1). Concerning the increasing demands of people for aesthetic prospects like decreasing the unwanted submental fat, evidence supports the effectiveness of noninvasive alternative procedures for liposuction and plastic surgery (2).

Amongst them, injection of deoxycholic acid (DCA) is a minimally invasive procedure. In 2015, the U.S. Food and Drug Administration (FDA) approved DCA, for treating fat beneath the chin (3). The mechanism of action of the drug is through the lysis of fat cell membranes and the physical destruction of cells (4)

The efficacy and safety of DCA in reducing the SMF have been demonstrated in multiple phase I to III clinical studies. (5). Phase I studies demonstrated that DCA administration did not significantly impact on liver function, kidney function, heart rate, or levels of cholesterol, triglycerides, free fatty acids, or proinflammatory cytokines (6,7). Phase II studies examined treatment regimens and dosages, revealing that the optimal dose for DCA was 2mg/cm² administered via 0.2 ml injections spaced 1 cm apart in the submental area. The recommended injection interval was 28 days (8, 9). Phase III studies have shown the efficacy and safety of DCA in SMF reduction. Accordingly, in a 12-week double-blind, placebo-controlled study including physician examinations, patient satisfaction, and MRI fat mass measurements, the clinical evaluation revealed that 70% of the individuals who received the medicine showed one grade of improvement in SMF score. Additionally, 13.4% of the subjects demonstrated two grades improvement, while no improvement was observed in the placebo group. These findings underscore the safety and effectiveness of the drug in treating moderate to severe submental fat. In the MRI evaluation, the proportion of responders was significantly higher in the intervention group compared to placebo group (46.3% vs. 5.3%; p < 0.001). Researchers concluded that DCA is an effective and safe injectable drug in reducing SMF (10).

The drug is administered to individuals aged 18 to 65. Common adverse events included pain, swelling, hematoma, and bruising at the injection site. There were some rare case reports, of damage to the mandibular nerve resulting in an asymmetric smile that generally resolves without any intervention (11). Another potential side effect is dysphagia, and the drug is contraindicated for individuals with a history of dysphagia (12).

The purpose of this study is the safety and efficacy assessment of Embella® injectable solution containing deoxycholic acid (manufactured by Espad Darou Pharmed Company) for the reduction of unwanted submental fat.

Objectives

Primary objective:

- Safety and efficacy assessment of Embella® injectable solution in reducing the unwanted submental fat.

Secondary objectives:

- Assessment of the efficacy of Embella® injectable solution, in improving the standard grading of submental fat (SMF)
- Assessment of the efficacy of Embella® injectable solution in reducing the diameter of submental fat
- Patient's satisfaction with the treatment process
- Pain assessment during the injection using a 11-point visual analogue scale
- Safety assessment of Embella® injectable solution

Study Method

It was a single group, before and after the clinical study. The study protocol as well as other essential documents (such as CRF, ICF, etc.) were approved by the Undersecretary of Research, Tehran University of Medical Sciences .

Also, all mentioned documents were approved by the ethics committee of Tehran University of Medical Sciences on 17 January 2023 (code: IR.TUMS.TIPS.REC.1401.102). The protocol was registered in the Iranian Registry of Clinical Trial Registry (IRCT) with registration number IRCT20190210042676N29.

Inclusion Criteria

- Age between 18 and 65 years old
- Individuals with any severity of unwanted submental fat
- Voluntarily signed the informed consent form and consented to the 3-month follow-up
- Willing to actively participate in the study and the scheduled visits

Exclusion Criteria

- Any previous interventions to treat SMF
- Anatomical features or previous trauma in the injection site which is liable to interfere with SMF evaluation or result in an aesthetically unacceptable outcome after treatment
- Evidence of any cause of submental enlargement other than SMF
- Patients with a body mass index (BMI) $> 30 \text{ kg m}^2$
- Those undergoing or considering a weight-reduction program
- Patients with a history of sensitivity to any components of the study medication or topical or local anesthetics
- Patients with a history of dysphagia
- Any inflammation, active infection, unhealed wound, or tissue scar at injection site
- Those using anticoagulants or NSAID or other medications that increase the risk of coagulation disorders within 7 days before injection
- Unrealistic expectations
- Pregnant or lactating women
- Those undergoing low sodium diets like hypertensive patients

Intervention

- Minimum 1 and maximum 3 treatment sessions (with at least 4 weeks intervals) with 2 ml of Embella® injectable solution, which contains 20 mg of DCA.
- 4 weeks after the first and second injections, the patient will be evaluated by the physician and research team. If necessary, they will receive additional injections; otherwise, they will proceed with post-injection follow-up.
- The product is a 2 ml sterile, transparent, and colorless vial containing 20 mg of DCA. Additional ingredients include hyaluronic acid, water for injection, sodium chloride, sodium hydroxide, hydrochloric acid, and disodium phosphate anhydrous.
- Use of ice/cold packs, topical and/or injectable local anesthesia (e.g., lidocaine) may enhance patient comfort.

Method of administration

The product is indicated for subcutaneous administration only.

[figure not shown]
EMBELLA® is supplied in ready-to-use, single-use vials. Gently invert the vial several times before use. Do not dilute.

EMBELLA® shall be prepared for injections in the following way:

1. Remove the flip-off cap from the vial and clean the penetrable stopper of the vial with an antiseptic. If the vial, seal, or flip-off cap is damaged, do not use it.
2. Attach a large bore sterile needle to a sterile single-use 1 ml syringe.
3. Introduce the large bore sterile needle into the stopper of the vial and draw 1ml of EMBELLA® into the 1ml syringe.
4. Replace the large bore needle with a 30 gauge (or smaller)-0.5-inch needle. Expel any air bubbles in the syringe barrel before injecting the product into the subcutaneous fat.
5. To withdraw the remaining contents of the vial, repeat steps 3 and 4.

[figure not shown]
For injection, the needle is inserted perpendicular to the skin, and injection should be avoided in the area defined by a line 1 to 1.5 cm from the angle of the mandible to the mentum (Figure 1).

Figure 1. Avoid the Marginal Mandibular Nerve Area

[figure not shown]
Avoid injection into the platysma. Prior to each treatment session, palpate the submental area to ensure sufficient submental fat and to identify subcutaneous fat between the dermis and platysma (pre-platysmal fat) within the target treatment area (Figure 2).

Figure 2. Sagittal View of Platysma Area

Outline the planned treatment area with a surgical pen and apply a 1 cm^2 injection grid to mark the injection sites (Figures 3).

Figure 3. Injection Pattern

WARNINGS AND PRECAUTIONS

- Embella[®] should only be injected within the defined parameters. Each vial is intended for use in one patient and should be discarded after use.
- Store the product between 15°C and 30°C.
- Use of ice/cold packs, topical and/or injectable local anesthesia, and NSAIDs may enhance patient comfort.

[figure not shown]
[figure not shown]
[figure not shown]
[figure not shown]
[figure not shown]
[figure not shown]
[figure not shown]
Endpoints

Primary and secondary endpoints are evaluated before injection and 4 and 12 weeks after the last injection.

Primary Endpoint

At least one-grade improvement in standard grading of submental fat (SMF) evaluated at 4 and 12 weeks after the last injection (Figure 4)

Figure 4: Standard grading of submental fat (SMF)

| Scale | 0 | 1 | 2 | 3 | 4 |
|----------------------------|---|---|--|---|---|
| Submental Convexity | Absent | Mild | Moderate | Severe | Extreme |
| Description | No localized submental fat evident | Minimal localized submental fat | Prominent localized submental fat | Marked localized submental fat | Extreme submental convexity |
| Representative Photographs |  |  |  |  |  |
| |  |  |  |  |  |
| |  |  |  |  |  |

Secondary Endpoints

- Submental fat diameter will be measured with the calliper at 4 and 12 weeks after the last injection
- Intensity of procedural pain will be assessed using the Visual Analogue Scale (VAS), ranges from 0 (complete painlessness) to 10 (maximum pain).
- Patient satisfaction will be assessed using the Visual Analogue Scale (VAS), ranges from 0 (not satisfied at all) to 10 (maximum satisfaction).
- Any observed or reported adverse events will be recorded after the injections and at 4 and 12 weeks follow-up visits, graded as mild [1] moderate [2] and severe [3].

Study Timeline

| Visit No | 0 | 1 | 2 | 3 | 4 | 5 | 6 |
|--|----------|-------------|---|---|------------------------|---|---|
| | Day 1 | | | | | | |
| Time | Baseline | Injection 1 | Week 4 (± 2 days) (Injection 2)/ Follow-up of subjects with a satisfactory response who do not require further treatment | Week 8 (± 4 days) (Injection 3)/ Follow-up of subjects with a satisfactory response who do not require further treatment | Week 12 ± 4 day | Week 16 ± 4 day (In subjects with 2 injections) | Week 20 ± 4 day (In subjects with 3 injections) |
| Screening | X | | | | | | |
| eligibility control | X | | | | | | |
| Consent | X | | | | | | |
| Demographic data | X | | | | | | |
| Injection | | X | X | X | | | |
| Pain assessment | | X | X | X | | | |
| Digital Photography | X | | X | X | X | X | X |
| Measurement of submental fat | X | | X | X | X | X | X |
| Patients' satisfaction | | | X | X | X | X | X |
| Physicians' assessment According to SMF | X | | X | X | X | X | X |
| Adverse Events | X | X | X | X | X | X | X |

Study Visits:

Visit 0: Screening & eligibility control

The following screening procedures will be conducted to determine eligibility: The investigator will evaluate each patient against the inclusion and exclusion criteria. If the patient is eligible to participate in the study, the study process will be explained to them in an understandable and verbal manner, and a consent form will be provided. Once the information presented to the patient has been thoroughly reviewed and understood by them, and they have received the necessary explanations, the patient will be asked to write their full name on the consent form and sign it. Following the completion of these steps, the following actions will be carried out:

- Digital AP and lateral photography of the patient's neck
- Grading of submental fat based on SMF
- Measurement of submental fat diameter

Visit 1 (day 1):

- Solution injection by the physician
- Monitor the patient for up to half an hour after injection
- Reporting and recording adverse events
- Pain assessment

Visit 2 (4 weeks±2 days):

In case of complete recovery with the physician's opinion:

- Digital AP and lateral photography of the patient's neck
- Grading of submental fat based on SMF
- Measurement of submental fat diameter
- Reporting and recording adverse events
- Evaluation the patient satisfaction

If re-injection is needed:

- Solution injection by the physician
- Monitor the patient for up to half an hour after injection
- Digital AP and lateral photography of the patient's neck
- Pain assessment
- Reporting and recording adverse events

Visit 3 (8 weeks±4 days):

In case of complete recovery with the physician's opinion:

- Digital AP and lateral photography of the patient's neck
- Grading of submental fat based on SMF
- Measurement of submental fat diameter
- Reporting and recording adverse events
- Evaluation the patient satisfaction

If re-injection is needed:

- Solution injection by the physician
- Monitor the patient for up to half an hour after injection
- Digital AP and lateral photography of the patient's neck
- Pain assessment
- Reporting and recording adverse events

Visit 4 (12 weeks±4 days):

- Digital AP and lateral photography of the patient's neck
- Grading of submental fat based on SMF
- Measurement of submental fat diameter
- Reporting and recording adverse events
- Evaluation the patient satisfaction

Visit 5 (16 weeks±4 days) (In subjectswith 2 injections):

- Digital AP and lateral photography of the patient's neck
- Grading of submental fat based on SMF
- Measurement of submental fat diameter
- Reporting and recording adverse events
- Evaluation the patient satisfaction

Visit 6 (20 weeks±4 days) (In subjectswith 3 injections):

- Digital AP and lateral photography of the patient's neck
- Grading of submental fat based on SMF
- Measurement of submental fat diameter
- Reporting and recording adverse events
- Evaluation the patient satisfaction

Participants:

This study will be conducted in 20 eligible participants.

Early Termination Policy: The decision to terminate the study early, due to safety concerns or to protect patient health, will be made by the Principal Investigator (PI) or the sponsor, with mutual agreement from both parties.

Withdrawal of Subjects

- The patients were allowed and free to refuse to cooperate with the study and follow-up whenever they want, but the researchers try to collect the maximum information, including the reasons for leaving the study and, if possible, the final results of the treatment.
- If a patient missed 2 or more consecutively scheduled visits, he/she was dismissed from the study.
- Occurrence of any of the exclusion criteria
- Occurrence of serious adverse event (SAE).

Data Collection

All required data will be recorded on the (paper) CRFs for this study, which will be designed and provided by PI. The reason for any missing data will be explained. All entries must be in permanent, blue ink. Errors will have single lines drawn through them with the correct data, recorder's initials, and date entered above the error. All errors must remain legible. Erasure or obliteration of errors in the CRF or other permanent study records are strictly prohibited.

Statistical analysis:

For statistical analysis, we performed descriptive statistics (mean, standard deviation or median and range, frequency and percentages). The efficacy of the treatment was assessed by comparing the mean/median value of each parameter among visits, using the Paired Sample T-test or the nonparametric equivalent, Wilcoxon test. SPSS 24 statistical software was used for data analysis. The statistical significance level was defined as $p<0.05$.

Adverse Events

Adverse Event (AE) is described as any medical event that occurs in patients participating in a study, which differs from the clinical manifestations of the underlying disease progression and does not necessarily have a causal relationship with the treatment used in the study. Clinical manifestations that will be reported as adverse events include any symptoms, signs (such as any abnormal laboratory results), or temporary illness related to the use of the product being studied, whether or not these effects are causally related to the product under study.

Very common adverse events of DCA include:

- Pain
- Edema
- Numbness, tingling,
- Swelling
- Bruising
- Redness of the skin (erythema)
- Itching

Common adverse events of DCA include:

- Injection site reaction
- Bleeding
- Pain and discomfort
- Flushing
- Change of skin color
- Nerve injury around the jaw
- Skin tightness
- Difficulties in swallowing (dysphagia)
- Feeling sick (nausea)
- Headache

Uncommon adverse events of DCA include:

- Unusual taste in the mouth

- Difficulties in speaking
- Hair loss (alopecia)
- Hives (urticarial)
- Skin sores (ulcer)
- Scar

Adverse events of DCA where the frequency is not known include (frequency cannot be estimated from the available data) :

- Reduced or abnormal sensation in the area of the mouth (e.g. lip, tongue)
- Reduced sense of touch or altered sensation in the cheek
- Tissue damage and cell-death (necrosis) around the treatment area
- Injury of blood vessels if injected accidentally into artery or vein

The medical conditions that existed prior to the start of the study are only considered as adverse events if they have worsened during the course of the study and cannot be attributed to the natural progression of the disease.

Serious Adverse Reaction (SAR) is described as a harmful response to an intervention and includes:

- result in death.
- pose a risk of death.
- require hospitalization.
- prolong the duration of hospitalization.
- cause persistent or significant disability.
- result in congenital anomalies or birth defects.
- require medical or surgical intervention to prevent permanent damage

Recording and Reporting of Adverse Events:

All adverse events and adverse drug reactions will be recorded in the patient's medical file as well as in the designated section of the CRF. They will be classified based on severity, relevance, and relation to the treatment used in the study, and in accordance with the investigator's criteria and the guidelines outlined below.

Classification of adverse events based on severity:

Adverse events will be classified according to their severity into three categories: mild [1], moderate [2], and severe [3], based on the following definitions:

Mild: Any reaction, sign, or symptom that the individual can recognize but does not influence performance or functioning.

Moderate: Any reaction, sign, or symptom(s) of a sufficient severity to make the subject uncomfortable. Performance of daily activities is influenced. This may require medical intervention.

Severe: Any reaction, sign, or symptom(s) of a sufficient severity to cause the subject severe discomfort. Performance of daily activities/functioning is compromised and causes disability and/or poses a specific risk to health. This usually requires medical intervention..

Note: Severe AEs are not necessarily serious unless one of the serious outcomes has occurred.

Classification of Adverse Events Based on Association with the Treatment Used in the Study: To determine the association between an adverse event or adverse drug reaction and the treatment used in the study, the following definitions will be considered:

-Certain: A clinical event involving changes in laboratory tests that are associated with a timely logical change in drug administration, and its occurrence cannot be explained by the person's current illness or other medications and substances. The response to drug reduction (dechallenge) should be clinically acceptable. This should be done from a pharmacological point of view and, if necessary, the drug re-exposure information (rechallenge) should be used .

-Probable: A clinical event involving changes in laboratory tests that are associated with a timely logical change in drug administration, and it is unlikely to be associated with a person's current illness or other medications and substances, and a reasonable clinical response is observed when the dose is reduced. There is no need for a rechallenge to put an undesirable event in this group.

-Possible: A clinical event involving changes in laboratory tests that are associated with a timely logical change in drug administration, but it can be justified by the person's current illness or other medications and substances. Drug reduction information maybe not available or may be ambiguous.

Unlikely: A clinical event involving changes in laboratory tests that are associated with a timely logical change in drug administration, and it is acceptable to justify its occurrence through current illness of the individual or other drugs and substances.

Conditional/Unclassified: A clinical event involving changes in laboratory tests, which is declared as an adverse reaction and it is necessary to obtain more data or more data are being evaluated for its correct evaluation.

Unassessable/Unclassifiable: A symptom that is probably an adverse reaction, but because the information about it is insufficient or inconsistent and related data cannot be confirmed or completed, it cannot be judged.

Quality Assurance:

This study and the accuracy of the tests at intervals were evaluated by [name]; the quality assurance manager based on the relevant SOPs.

Accordance with GCP:

The study was conducted according to the principles provided by Good Clinical Practice (GCP) and the Declaration of Helsinki

References:

1. ASDS Consumer Survey on Cosmetic Dermatologic Procedures. 2018; Available at: <https://www.asds.net/Medical-Professionals/> Practice-Resources/ASDS-Consumer-Survey-on-Cosmetic Dermatologic- Procedures. Accessed
2. Liu, Michael, Cameron Chesnut, and Gary Lask. "Overview of Kybella (deoxycholic acid injection) as a fat resorption product for submental fat." *Facial Plastic Surgery* 35.03 (2019): 274-277.
3. <https://www.fda.gov/drugs/drug-approvals-and-databases/drug-trials-snapshots-kybella>

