- Pain
- Edema
- Numbness, tingling,
- Swelling
- Bruising
- Redness of the skin (erythema)
- Itching

Common adverse events of DCA include:

- Injection site reaction
- Bleeding
- Pain and discomfort

- Flushing
- Change of skin color
- Nerve injury around the jaw
- Skin tightness
- Difficulties in swallowing (dysphagia)
- Feeling sick (nausea)
- Headache

Uncommon adverse events of DCA include:

- Unusual taste in the mouth
- Difficulties in speaking
- Hair loss (alopecia)
- Hives (urticarial)
- Skin sores (ulcer)
- Scar

Adverse events of DCA where the frequency is not known include (frequency cannot be estimated from the available data) :

- Reduced or abnormal sensation in the area of the mouth (e.g. lip, tongue)
- Reduced sense of touch or altered sensation in the cheek
- Tissue damage and cell-death (necrosis) around the treatment area
- Injury of blood vessels if injected accidentally into artery or vein

The medical conditions that existed prior to the start of the study are only considered as adverse events if they have worsened during the course of the study and cannot be attributed to the natural progression of the disease.

Serious Adverse Reaction (SAR) is described as a harmful response to an intervention and includes:

•result in death.

•pose a risk of death.

•require hospitalization.

- prolong the duration of hospitalization.
- cause persistent or significant disability.
- result in congenital anomalies or birth defects.
- require medical or surgical intervention to prevent permanent damage

Section 5: Statistical analysis

Patient Characteristics and Baseline Comparisons

Basic characteristics are described using mean and standard deviation (SD) or median and range, frequency and percentages.

Primary and Secondary Endpoint Analysis

Descriptive analysis is performed using mean, SD or median and range, frequency and percentages. The efficacy of the treatment is assessed by comparing the mean/median value of each parameter among visits, using the Paired Sample T-test or the nonparametric equivalent, Wilcoxon test. The statistical significance level is defined as $p < 0.05$.

Safety Analysis

All adverse events and adverse drug reactions will be recorded in the patient's medical file as well as in the designated section of the CRF. They will be classified based on severity, relevance, and relation to the treatment used in the study, and in accordance with the investigator's criteria and the guidelines outlined below.

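### Jaw-nerve injury is labelled rare in one place and common in two others; separately, no visit describes a directed check for it, so zero events in 20 would reassure even less than the sample size allows

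*Protocol*

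**What the plan says.** **Frequency.** The Protocol Introduction, in its account of the drug class, says "There were some rare case reports, of damage to the mandibular nerve resulting in an asymmetric smile" and adds that this "generally resolves without any intervention". Its sentence on common events does not include nerve damage: "Common adverse events included pain, swelling, hematoma, and bruising at the injection site". Under Adverse Events, the Protocol lists "Nerve injury around the jaw" in the common group, together with dysphagia. The SAP repeats that list under Safety End point, headed "Common adverse events of DCA include". Neither document attaches a percentage to any of the frequency words.

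**Collection.** The Protocol's Secondary Endpoints state: "Any observed or reported adverse events will be recorded after the injections and at 4 and 12 weeks follow-up visits". The study timeline marks AEs at every visit from 0 to 6. The visit lists after screening each contain a generic line for AE recording, and injection visits add up to half an hour of monitoring. None names an examination of facial movement or a question about swallowing. Photographs are front and side views of the neck. In the re-injection branches of Visits 2 and 3, AE recording is listed after the injection.

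**Standing of safety.** Safety is part of the primary objective. The Method of administration section recognises the nerve hazard by defining an area where injection is to be avoided. The SAP grades AEs by severity, and its general descriptive methods include frequencies and percentages. It specifies no confidence interval for any AE.

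**The concern.** There are two separate matters.

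First, a reader cannot tell from the documents whether a jaw-nerve injury among 20 subjects would be expected or surprising. The Introduction suggests surprising; the two lists suggest it would not be.

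Second, the plan depends on general AE recording for an event that it describes as usually self-resolving. After the half-hour of observation, the next listed visit is about 4 weeks away. A mild asymmetry could begin and resolve in that interval, and would then be recorded only if the subject mentioned it or was asked. The plan does not say that anyone asks. At a re-injection visit, the listed order also does not secure a record of nerve and swallowing status before the next dose.

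At stake is how a report of no nerve injuries should be read. With 20 subjects it is weak evidence in any case, and under-recording would weaken it further by an unknown amount.

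**Working it through.** The documents give no rate for nerve injury and no derivation of the sample size, so there is no plan figure to reproduce. The frequency bands and the capture fraction below are assumptions.

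**Inputs**
- N = 20 (Protocol, Participants; SAP, Sample size).
- Common: assumed 1% to 10% of subjects.
- Rare: assumed 0.01% to 0.1% of subjects.
- Capture fraction s, the share of true cases that reach the record: assumed 1, 0.75 or 0.5.

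**Step 1: does the label matter at N = 20?** Expected cases are 20p, and the chance of at least one case is 1 − (1 − p)^20.

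| Assumed true rate p | Expected cases | Chance of at least one |
|---|---|---|
| 0.01% (rare, low) | 0.002 | 0.2% |
| 0.1% (rare, high) | 0.02 | 2.0% |
| 1% (common, low) | 0.2 | 18.2% |
| 4% (common, middle) | 0.8 | 55.8% |
| 10% (common, high) | 2 | 87.8% |

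Under the rare label a case is very unlikely. Under the common label the chance runs from 18% to 88%, so even then a case is not assured.

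**Step 2: what would 0/20 show with complete recording?** The exact two-sided 95% upper limit is 1 − 0.025^(1/20) = 0.168, or 16.8%. The one-sided 95% limit is 1 − 0.05^(1/20) = 0.139, or 13.9%. Either limit lies above both assumed bands, so zero cases could not tell common from rare.

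**Step 3: what does incomplete recording do?** If a fraction s of cases is captured, the recorded rate is s·p.
- The chance of recording at least one case is 1 − (1 − s·p)^20. With s = 0.5, the figures for p = 1%, 4% and 10% fall from 18.2%, 55.8% and 87.8% to 9.5%, 33.2% and 64.2%.
- The 16.8% limit applies to the recorded rate. The limit on the true rate is 0.168/s: 0.1684/0.75 = 22.5% for s = 0.75, and 0.1684/0.5 = 33.7% for s = 0.5.

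**Step 4: which defect has which effect?** The label conflict changes what to expect (Step 1). It does not alter what is recorded. Any under-recording would come from the absence of a directed check (Step 3). The two need separate corrections.

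**The case against.** The strongest reply is that collection is more structured than the endpoint wording suggests. AE recording is scheduled at every visit. All AEs go to the medical file and the CRF. Jaw-nerve injury and dysphagia are both named as expected events, and the AE definition extends to temporary illness. The Protocol's Intervention section also has the physician and research team evaluate the patient 4 weeks after the first and second injections, before deciding on another. All of this stands. A reader might infer that events enter the record only if volunteered, that a transient palsy leaves no trace, or that nothing is assessed before re-injection. The documents do not support any of these. They leave open whether subjects are asked, and they do not fix when AEs are recorded relative to the injection.

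The CRF is a separate document, not available here, and may already contain a checklist. That also stands, and the fix is conditional on it.

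The two risk descriptions may differ in scope: the Introduction concerns mandibular nerve damage with an asymmetric smile, while the lists use a broader, undefined term. That is possible, but neither document says so, and reconciliation would settle it.

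Finally, the Introduction calls pain, swelling and bruising common where the lists call them very common, and it names hematoma where the lists do not. These differences carry little weight. The Introduction is narrative prose, and the lists include bruising, bleeding and injection site reaction.

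**Conclusion.** The point holds in two limited parts. The frequency wording for jaw-nerve injury is inconsistent between the Protocol Introduction and the AE lists in both documents, and it must be reconciled. This alone is nearly clerical, because no endpoint, test or sample size uses either label. Separately, the described procedures contain no directed check for nerve weakness or swallowing difficulty, so transient cases may be under-recorded. That makes zero events in 20 weaker reassurance than the 16.8% upper limit already implies; with half of cases captured, the limit would be about 34%.

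A reader might go further and conclude that the trial will miss its key safety event, or that a zero count could not be interpreted. Neither follows. The documents do not single out nerve injury as the key event, and whether a case is likely depends on a rate they do not give. A zero count still has a meaning: it bounds the rate, though loosely. The looseness at 16.8% comes from N = 20, and better ascertainment would not narrow it. Better ascertainment would make that limit apply to the true rate.

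The numerical statements rest on the assumed bands and capture fractions; the 0/20 limit rests only on N = 20. This is an inexpensive improvement and not a flaw that undermines the trial.

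**What to change.** 1. Reconcile the Protocol Introduction with the AE lists in the Protocol and SAP against the sponsor's source. State what the frequency words mean numerically and whether the two nerve terms cover the same event, and carry one description through all risk text.
2. Unless the CRF already has them, add two fixed yes/no AE items: asymmetric smile and difficulty swallowing. Each should ask about the visit day and the time since the last visit, with onset and resolution dates. The recall part is essential, because a check confined to the visit day would miss a palsy that had already resolved.
3. Take a baseline at Visit 0, and complete the items before any injection at Visits 2 and 3. This fixes only when the data are recorded; it sets no rule for re-injection. If the CRF already contains such items, cite them in the Protocol.
4. In the SAP, report each event as n/20 with an exact 95% CI.

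A smiling photograph is optional, since it too shows only the visit day.

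The cost is about a minute per existing visit, and possibly a higher recorded event rate than general AE recording would give. If visits are already complete, items 1 and 4 can still be done, and the report should state the limit on ascertainment.
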